2.4 The PREHAB Study – Primary Research Questions/Hypotheses

The primary research question(s) for the *Prehab* study include:

- i. What is the effect of a preoperative cardiac pre-habilitation (“*Prehab*”) program on the proportion of patients with hospital length of stay (*LOS*) > 7 days.
We hypothesize that the performance of a multifaceted, interdisciplinary cardiac “*Prehab*” program in patients awaiting an elective cardiac surgery will reduce the proportion of frail elderly patients requiring a postoperative hospital *LOS* > 7 days.
- ii. What is the effect of a preoperative cardiac pre-habilitation program in high-risk frail elderly patients on (1) pre-operative frailty, (2) exercise capacity, (3) self-managed physical activity behavior, (4) in-hospital outcomes, (5) 3-month clinical outcomes, and (6) 3 month health-related quality of life.
We hypothesize that the “*Prehab*” program for frail elderly patients awaiting an elective cardiac surgery will reduce frailty, improve exercise capacity, improve self-managed physical activity behavior, improve in-hospital outcomes, improve clinical outcomes 3 months and 1 year postoperatively, and improve health-related quality of life.

3 Study Design

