3.5.2 Safety and Baseline Assessments

A medical director, at each site, will oversee all cases and ensure patient eligibility and safety for program initiation and throughout program attendance for the study duration. All eligible and consented patients will be evaluated at baseline to ensure angina stability. Exercise prescription will be determined utilizing the standard practice of the Karvonen Equation adjusted according to pre-program exercise stress test. (21)Patients will also undergo a standard *6MWT* (73)(74)(75)(76)(77)(78) and will repeat the *6MWT* at the preoperative time point in both the control and *Prehab* groups to determine impact of the intervention. The *6MWT* was chosen because it requires minimal infrastructure and personnel to complete and has been demonstrated to be a valid prognostic tool for patient outcomes and is comparable to an exercise-stress test. (73)(75)(76)(77)This approach enables us to avoid potential scheduling issues that occur if a patient’s surgical date is moved up.

Patients who are deemed appropriate for enrolment into study will be randomized, following the completion of the baseline data collection, to one of two trial arms – control (standard of care (*StandC*) or treatment (*Prehab*). Baseline risk factor evaluation, anthropometrics, clinical markers, patient questionnaires (including frailty scores, cognitive assessment, and quality of life data) and physical activity data measured using accelerometers will be collected for all patients and repeated pre-operatively and at three-month follow up. Safety data including new hospitalization, worsening angina or heart failure and arrhythmias will be captured and all adverse events will be reportable to the study Data Safety Monitoring Board (*DSMB*). All patients in both groups will be referred to postoperative *CR* programming, as per local practice.

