Briefly, patients will be required to attend a minimum of 2 structured exercise sessions per week. The program will last a total of 8 weeks, or until the patient undergoes their cardiac procedure (minimum of 4 weeks for data collection purposes). Patients will be encouraged to walk daily in addition to attending the scheduled exercise sessions. Exercise will be prescribed according to standardized procedures at the medical fitness facility for their cardiac rehabilitation program. Briefly, participants will complete a warm-up/stretching session of approximately 15 minutes at the beginning of each session. Aerobic exercise will be prescribed at 40-60% of heart rate reserve (Karvonen Formula) based on baseline exercise stress test data. Aerobic exercise will last approximately 10-30 minutes depending on individual tolerance and level of conditioning. Aerobic prescription will progress to high intensity exercise in the context of symptom-limited, interval training up to 85% of maximal aerobic capacity based upon recommendations by the cardiologist. Individual interest will determine the modality of exercise chosen. Options will include walking, cycling, stretching and resistance training with body weight or resistance bands following clearance by a cardiologist. Intensity will be progressed based on close communication between healthcare providers and participants. Sessions will be concluded with a 10-minute cool down period.

In addition to the exercise program, patients will be required to participate in 4 educational sessions tailored to self-management for cardiac rehabilitation. Examples of educational sessions offered by professional staff at the medical fitness facility include:

- Exercise and Action Planning (Kinesiologist)
- Risk Factor Modification (Nurse/Physiotherapist)
- Cardiac Electrical System (Nurse/Physiotherapist)
- Cardiac Circulation (Nurse/Physiotherapist)
- Cardiac Muscle Function (Nurse/Physiotherapist)
- Resistance Training (Kinesiologist)
- Body-Mind Connection (Social Worker)

“The PREHAB Study” (Pre-operative Rehabilitation for reduction of Hospitalization After coronary Bypass and valvular surgery.)

Heart Healthy Eating (Dietician)
Looking Forward; transitions, barriers, self-management (Kinesiologist)
Diabetes Education (Dietician)
Emotional Impact of Heart Disease (Social Worker)
Label Reading (Dietician)
Preventing Relapse (Social Work)
Stress Busters (Psychologist)
Tracking Food Choices (Dietician)

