Smoking Cessation (Social Worker)
Relaxation Techniques (Psychologist)

Participants in the intervention group will be asked to keep a log of their attendance at both the exercise and educational session. Additionally, an exercise log completed by individual patients will track the mode of exercise completed in addition to monitoring compliance with the intervention.

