5.1.2 Secondary Outcomes

(1) pre-operative frailty, (2) exercise capacity, (3) physical activity behavior, (4) in-hospital outcomes, (5) 1-year clinical outcomes, (6) 1-year health-related quality of life, (7) cost-analysis.

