5.2 Statistical/Analytical Plan

Objective 1: To determine if *Prehab* reduces the proportion of frail elderly patients requiring a prolonged hospital length of stay of >7 days. A univariable analysis will be undertaken to determine if hospital *LOS* > 7 days is associated with frailty and other patient-level factors. A stepwise multivariable logistic regression model will then be developed to determine if *Prehab* attendance is independently associated with a decreased risk of prolonged hospital length of stay > 7 days. As a secondary analysis, hospital *LOS* will also be compared as a continuous variable between the *Prehab* and standard care groups using a Mann-Whitney test.

“The PREHAB Study” (Pre-operative Rehabilitation for reduction of Hospitalization After coronary Bypass and valvular surgery.)

Objective 2: Does attending *Prehab* influence frailty, exercise capacity, physical activity behavior, in-hospital complications, and *HRQoL*? Although we will employ four different measures of frailty, based on our preliminary data and based on a Task Force’s position statement(90), the Modified Fried Criteria will be the primary frailty outcome over time from baseline to the end of *Prehab* program (pre-operatively), or from baseline to the 3-month post-operative follow-up. The primary measure of exercise capacity will be the *6MWT* and will be analysed with univariable linear regression models to evaluate the association between the *6MWT* and *Prehab* attendance. Accelerometers will be used to objectively measure the number of minutes spent performing moderate to vigorous physical activity (*MVPA*) and total physical activity (*TPA*) per day for a period of 7 days and compared between groups. A composite outcome for a major adverse cardiac event (i.e. *MACCE* = in-hospital stroke, myocardial infarction, renal failure requiring dialysis and death) and delirium will be compared between groups using a Chi-Square or Fisher’s Exact test. A multivariable logistic regression will be used to identify if *Prehab* is independently associated with in-hospital delirium. The *SF-12v2* and *EQ-5D* scores, after normative standardization, will be analyzed through use of a repeated *ANOVA* to allow for a standardized group and group/time interaction effect estimation.

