Intervention: Standard care: three-hour preassessment appointment. Prehab: exercise and education classes for 60 minutes/day, twice weekly for at least four weeks.

Main measures: Data were collected at baseline, one week preoperatively, and three months postoperatively. The primary outcome measure was walking distance using a 6-minute walk test. Secondary outcome variables included 5-meter gait speed, and cardiac rehabilitation attendance three months postoperatively.

Results: Fifteen patients (standard care, $n = 7$; Prehab, $n = 8$) completed the study. No Prehab patients developed cardiac symptoms during study participation. Walking distance remained unchanged in the standard care group; whereas, the Prehab group increased their walking distance to mean \pm SD 474 \pm 101 and 487 \pm 106 m at the preoperative and three month postoperative assessments ($p < 0.05$). Gait speed was unchanged in the standard care group, but improved in the Prehab group by 27% and 33% preoperatively and three months postoperatively, respectively ($p < 0.05$). Enrollment in cardiac rehabilitation three months postoperatively was higher for Prehab participants (100%) than standard care participants (43%; $p < 0.05$).

¹Faculty of Nursing, University of Manitoba, Winnipeg, Canada

²Health, Leisure, and Human Performance Research Institute, Faculty of Kinesiology and Recreation Management, University of Manitoba, Winnipeg, Canada

³Institute of Cardiovascular Sciences, St. Boniface Hospital Research Centre, Winnipeg, Canada

⁴Reh-Fit Centre, Winnipeg, Canada

⁵Department of Surgery (Cardiac Surgery), University of Manitoba, Winnipeg, Canada

⁶Department of Physiology, University of Manitoba, Winnipeg, Canada

Corresponding author:

[name], Health, Leisure, and Human Performance Research Institute, Faculty of Kinesiology and Recreation Management, University of Manitoba, [name], Canada.
Email: [contact]

Conclusion: These data provide evidence for the feasibility of a Prehab intervention to improve the health status of patients waiting for elective CABG surgery. A larger trial of 92 patients will be utilized to demonstrate the safety and efficacy of Prehab.

Keywords

Coronary artery bypass, exercise therapy, pre-habilitation

Received: 26 August 2013; accepted: 16 November 2013

Introduction

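### Before surgery, total accelerometer minutes include supervised Prehab classes for patients still in the programme, so they cannot by themselves show better self-managed activity

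*Combined protocol and SAP*

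**What the plan says.** Section 2.4 lists, among the things Prehab may change, "3) self-managed physical activity behavior", and its hypothesis repeats the self-managed wording. Section 5.1.2 drops the qualifier: "3) physical activity behavior, (4) in-hospital outcomes". Section 5.2 then defines the measure: "Accelerometers will be used to objectively measure the number of minutes spent performing moderate to vigorous physical activity", together with total physical activity, "per day for a period of 7 days and compared between groups". It gives no time point, no test and no rule for class time.

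Section 3.5.2 sets the timing: "physical activity data measured using accelerometers will be collected for all patients and repeated pre-operatively and at three-month follow up". Section 3.6 places the pre-operative visits one week before surgery.

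Section 3.5.5 runs the programme for 8 weeks or until surgery, with at least two structured sessions a week. On session content it says: "Aerobic exercise will last approximately 10-30 minutes depending on individual tolerance and level of conditioning". It also says: "Participants in the intervention group will be asked to keep a log of their attendance at both the exercise and educational session". Nothing links that log to the accelerometer analysis. Section 3.5.4 gives standard-care patients no classes and says they are advised to rest and keep to very light activity.

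**The concern.** The hypothesis is about what patients do on their own initiative. The measure counts all movement, including exercise that the trial itself delivers to one arm. If the pre-operative wear week falls while the programme is running, class minutes enter the Prehab total and nothing comparable enters the standard-care total. The arms can then differ even if no patient does anything more outside class, and the error favours Prehab. What is at stake is the interpretation of one secondary outcome: delivery of the intervention could be reported as a change in self-managed behaviour.

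**Working it through.** **Figures in the plan.** The documents give no effect size or power for the accelerometer outcome. The only sample-size figure is for the primary outcome. It reproduces: 58.3% versus 38.3%, two-sided 5%, 80% power gives 97 per arm, and 97/0.80 = 121.25, rounded up to 122. It is used below only as a number of patients per arm.

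**Does the wear week overlap the programme?** Section 3.5.6 (Variable Waitlist Time) gives a median wait of 62 days in the preliminary study. A visit one week before surgery then falls on day 62 - 7 = 55. An 8-week programme started on day 0 ends on day 56, and a later start ends later. A patient with the median wait is therefore still in the programme at that visit. With the 12-week Manitoba median (84 days), the visit falls on day 77, and the programme is still running only if it began after day 77 - 56 = 21. Overlap is likely for many patients but not for all.

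**Class minutes.** 2 classes x 10-30 aerobic minutes = 20-60 min/week (2.9-8.6 min/day). Section 3.5.5.6 describes 1-hour sessions, so 120 min/week is an upper bound if every minute counted.

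**Pilot baselines** (pilot manuscript Table 3; standard care n = 6, Prehab n = 7; min/week):

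| Measure | Pooled baseline | 20-60 min as a share |
|---|---|---|
| MVPA, sporadic | (132x6 + 139x7)/13 = 135.8 | 15-44% |
| MVPA, 10-minute bouts | (82x6 + 21x7)/13 = 49.2 | 41-122% |
| Total activity, sporadic | (576x6 + 574x7)/13 = 574.9 | 3-10% |

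Section 5.2 states no bout rule, so the first two rows are both possible readings of MVPA.

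**Chance that class time alone gives p < 0.05 on sporadic MVPA.** Power = Φ(d/(SD x √(2/97)) - 1.96), where d is the class minutes per week averaged over the Prehab arm. The pilot baseline spread of ±64 is labelled SD in the manuscript and standard error in the protocol's own accelerometry table. Both are tried; the second gives SD = 64 x √7 = 169.

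| Share of Prehab arm still in class | SD 64: 20 / 60 min | SD 169: 20 / 60 min |
|---|---|---|
| All | 59% / >99% | 13% / 70% |
| Half | 19% / 90% | 6% / 23% |

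This assumes 97 patients per arm with usable data, every aerobic class minute registering as MVPA, no other activity displaced, and no change in self-managed activity in either arm.

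**The case against.** - **Total minutes are a valid measure of physical activity behaviour**, which is how 5.1.2 and 5.2 name the outcome. This stands, and total minutes should stay. They still do not answer the narrower question in 2.4. The Paffenbarger scale and the exercise self-efficacy questionnaire (3.4.8) offer other evidence, so the trial is not silent on self-management.
- **Not every patient is affected.** This stands. Some will have finished the programme before the wear week. Section 3.5.5.6 makes weeks 5-8 looser, with frequency chosen by the patient, while 3.5.5 asks for two supervised classes a week throughout. For a patient with a long wait, the wear week falls in those later weeks, so class time could be below the figures above.
- **Pre-operative data may be sparse.** In the pilot, 11 of 15 patients had surgery within 1-3 days of notice and pre-operative accelerometry was not analysed. This limits the comparison but does not remove the ambiguity in whatever data are obtained.
- **The 10-minute-bout percentage uses the smallest denominator.** This is fair, so the sporadic and total-activity figures are shown beside it.

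A reader might extend the point to 3 months, because pilot rehabilitation enrolment was 100% against 43%. The documents do not support that. Section 2.2 says both arms are referred and attend voluntarily, and 3.1.1.2 presents higher enrolment as evidence of lasting self-management. Those minutes are arguably part of the effect sought. Nor did the pilot show an excess in sporadic MVPA at 3 months: 250 min/week in Prehab against 281 in standard care, with a difference in change of -37 (95% CI -274 to 198). That interval is too wide to settle the matter either way.

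**Conclusion.** The point holds for the pre-operative comparison and for patients still in the programme during the wear week. For them, supervised classes contribute about 20-60 aerobic min/week, or 15-44% of pooled pilot sporadic MVPA and 3-10% of sporadic total activity. A significant difference from class time alone ranges from unlikely to near certain, depending on the pilot spread and on how many patients are still attending. A pre-operative difference in total minutes therefore cannot by itself support the self-managed claim.

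A reader might go further and infer that a difference is guaranteed by design. The documents do not support this: they never say that the accelerometer is worn in class. The overlap follows from the timing and from the absence of an exclusion rule, and its extent is unknown. The percentages rest on 13 pilot patients. This is an inexpensive improvement to one secondary outcome; the primary outcome and sample size are untouched.

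**What to change.** 1. In 5.2, name the accelerometer time points.
2. For the pre-operative comparison, report MVPA and total activity per day in two versions: all minutes, and minutes outside supervised Prehab sessions. Base any statement about self-managed activity on the second.
3. Add session date and start and end time to the attendance log in 3.5.5, so that class time can be masked.
4. Where only class days are known, use the average over non-class days as a sensitivity analysis only, because it drops days in one arm.
5. At 3 months keep total minutes and report rehabilitation enrolment alongside.
6. Align the outcome wording in 2.4, 5.1.2 and 5.2.
7. Reconcile 3.5.5 with 3.5.5.6 on how far weeks 5-8 are supervised, so that session time can be defined.

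The cost is one extra log field, a short SAP edit and simple programming. The drawbacks are slightly fewer usable minutes in the Prehab arm and probably a smaller pre-operative difference.

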3.4.3 In-Hospital Outcomes

Postoperative *ICU* and hospital *LOS*, 30-day mortality, major adverse events (death, *MI*, stroke or renal failure requiring dialysis) will be collected using existing site surgical databases. Post-operative *CR* enrollment will be assessed using administrative data from the participating *CR* centers.

In our preliminary analysis, we have identified a strong association between frailty and the occurrence of delirium (Table 5). The participating Cardiac *ICUs* currently perform an agitation and delirium assessment once every 8 hours as standard practice. Delirium assessment will be performed in the *ICU* using the Richmond Agitation-Sedation Scale (*RASS*)(59) and the Confusion Assessment Method for the Intensive Care Unit (*CAM-ICU*). (60)(61)(62). As part of standard of care a blood sample will be collected upon placement of the arterial line in the operating room to ascertain the patient’s sodium, potassium, glucose, white blood cell count, hematocrit, creatinine and albumin and this data will also be collected.(49)(65)

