3.6 Data collection

All participants will meet with the research staff at nine time points: 1) twice at time of enrolment after their acceptance for a surgical procedure (i.e. baseline pre-intervention); 2) 4 weeks following randomization into either standard care or intervention group; 3) twice, 1-week

“The PREHAB Study” (Pre-operative Rehabilitation for reduction of Hospitalization After coronary Bypass and valvular surgery.)

preoperatively (i.e. Pre-op); 4) twice, 3 months postoperatively; and, 5) twice, 1 year postoperatively (Figs. 4 and 5). Data collection will occur from both written and electronic medical records sources (i.e. patient information systems, where applicable). Existing perioperative surgical, *ICU* and hospital data will be used to capture patient demographics, procedure urgency, intraoperative procedure and anesthetic variables, cardiopulmonary bypass information, blood product utilization, mechanical ventilation, delirium/coma, *ICU* and hospital *LOS*, major adverse events, infection and *ICU* and hospital recidivism are collected in institutional databases.

Patients deemed “unsafe” to be enrolled in the exercise portion of the study or that have refused to be randomized but have consented to participate in the follow up registry will be contacted via telephone by research staff after their surgeries at two time points: 1) 3-months after surgery; and, 2) 12-months after surgery. A data sharing agreement, in compliance with provincial patient confidentiality legislation will be created to permit planned analysis. We have previously utilized these data collection methods.(49)(65)(88)(89)(90)

4 Safety Monitoring

Safety data including new hospitalization, worsening angina or heart failure and arrhythmias will be captured and all adverse events will be reportable to the study Data Safety Monitoring Board (*DSMB*). The *DSMB* is an independent group of experts that advises study investigators. They are responsible to periodically evaluate the study data for participant safety and study conduct, in addition to making recommendations concerning the modification and/or termination of the trial.

Safety Monitoring: Clinical stability during the pre-habilitation period is to be evaluated twice per week by the *CR* team using clinical questioning in comparison to their baseline stress test. All cases will be reviewed in conjunction with the attending physician.

5 Statistical Analysis Plan

5.1 Measures/Outcomes:

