participants. Over the past decade, length of stay following elective cardiac surgery has declined from an average seven days to five days,²² which coincides with the average length of hospital stay in our study. Therefore, recent advances in surgical procedures, as well as a small sample size in the current study, could account for the differences observed in our study, as compared with the cardinal study by Arthur et al. published in 2000, where they found a reduction in the length of hospital stay of one day.

Our data shows that all eight (100%) of the Prehab patients chose to enroll in cardiac rehabilitation postoperatively, which was significantly different from the three (43%) standard care patients who chose to enroll. These data add to the previous literature, where Arthur et al.⁸ found that CRP attendance rates postoperatively were 70% among Prehab participants, and only 57% among standard care participants. Collectively, a Prehab intervention for elective CABG surgery patients could enhance CRP attendance postoperatively because current estimates indicate that only 15%–20% of North Americans of the referred cardiac population chooses to enroll.²³ However, we acknowledge that only 29% of the eligible elective CABG surgery patients who were contacted chose to participate in the study (Figure 1).

This pilot study has several limitations. The research assistant was not blinded to which participants were in each group, thus increasing detection bias. However, data collection by the research assistant was conducted in accordance with standardized procedures for each outcome variable. In the context of generalizability, beta-blocker use was significantly higher in the standard care group compared with the Prehab group. Furthermore, our recruitment criteria limited us to 79/297 (27%) of the elective CABG surgery cohort. We also did not recruit patients scheduled for other surgeries (i.e. valve repair/replacement, combination surgeries); however, this was a safety feature of our study based on the consensus of cardiac surgeons and cardiologists at the hospital site, that the lack of supportive evidence concerning the safety of a Prehab intervention warranted the exclusion of more complex procedures.

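### The one specified between-arm comparison of major adverse events is in-hospital, so events between randomization and surgery enter no planned analysis by arm

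*Combined protocol and SAP*

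**What the plan says.** Section 5.2, Objective 2, defines MACCE as "in-hospital stroke, myocardial infarction, renal failure requiring dialysis and death" and states that it, together with delirium, "will be compared between groups using a Chi-Square or Fisher’s Exact test". No other between-arm comparison of major clinical events is written there. Section 3.4.3, headed In-Hospital Outcomes, lists the same four events and their source: "major adverse events (death, *MI*, stroke or renal failure requiring dialysis) will be collected using existing site surgical databases".

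For safety, Section 4 says: "Safety data including new hospitalization, worsening angina or heart failure and arrhythmias will be captured". The Synopsis and Section 3.5.2 repeat this. All adverse events are reportable to the DSMB, whose members have this task: "They are responsible to periodically evaluate the study data for participant safety and study conduct". Neither Section 5.1.2 nor Section 5.2 gives these data a summary by arm, a denominator or a time window.

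Other event outcomes are named without a method in Section 5.2: 30-day mortality (3.4.3), readmission at 30 days and 12 months (3.4.9) and 1-year clinical outcomes (5.1.2). Section 2.4 places the 3-month and 1-year clinical outcomes after surgery. Section 3.2 commits the trial to intention-to-treat analysis.

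**The concern.** The intervention ends at surgery. Prehab patients do supervised exercise that progresses towards high-intensity intervals (Section 3.5.5), while controls are advised to rest and keep to very light activity (3.5.4). After surgery both arms are referred to the same rehabilitation (2.2, 3.5.2). Harm from the exercise itself, if there were any, would be expected mainly before surgery, and that is the interval the MACCE comparison leaves out.

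The prior evidence on this programme is thin. The pilot manuscript in the appendix reports no adverse events during Prehab in eight patients. It left out valve and combined operations because "the lack of supportive evidence concerning the safety of a Prehab intervention warranted the exclusion of more complex procedures". Section 3.3.1 of this protocol enrols those operations.

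At stake is what the trial can say about safety. It could report equal MACCE in the two arms whatever happened while patients waited, and readers would have no planned figure to set beside it.

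**Working it through.** **The plan's own figure.** The documents give no number for the adverse-event comparison. The sample size (Section 5.3) supplies the number per arm. With 58.3% against 38.3%, two-sided alpha 0.05, power 80% and pooled variance:

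n = [1.960·√(2·0.483·0.517) + 0.842·√(0.583·0.417 + 0.383·0.617)]² / 0.20² = (1.385 + 0.583)² / 0.04 ≈ 96.8, so 97 per arm (194).

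Allowing for 20% dropout: 97/0.80 = 121.25, so 122 per arm (244). Both figures reproduce.

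**Who falls outside the comparison.**
- A patient who has an MI or stroke while waiting and is later operated on enters the surgical stay, but the earlier event is not in-hospital MACCE.
- A patient who dies while waiting, or is never operated on, has no surgical stay in which MACCE can be assessed.

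Both were randomized, so an analysis of the surgical stay alone does not cover the intention-to-treat population for major events.

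**What zero events would show.** The one-sided 95% upper limit for 0 events in n patients is 1 − 0.05^(1/n).
- Pilot, 0 of 8: 1 − 0.05^(1/8) = 31%. Section 3.1.1.2 counts seven Prehab patients, which gives 35%.
- This trial, if 0 of 122: 1 − 0.05^(1/122) = 2.4%.

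The trial could therefore supply a far tighter bound, but the plan does not ask for it.

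**Illustration of direction and scale.** Table 6 gives an in-hospital major event rate of 4/72 = 5.6% in frail patients. Assume that rate m in both arms, so the planned comparison has an expected difference of 0. Let r be the pre-operative risk. The documents give no value for r, so every value below is an assumption. Risk from randomization = r + (1 − r)·m; difference = (r_Prehab − r_control)·(1 − m). The last column is the exact power of Fisher's test on the pre-operative events alone, at 122 per arm.

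| Assumed r, control vs Prehab | From randomization | Difference | Expected patients of 122 | Power |
|---|---|---|---|---|
| 1% vs 3% | 6.5% vs 8.4% | 1.9 points | 7.9 vs 10.2 | 6% |
| 1% vs 5% | 6.5% vs 10.3% | 3.8 points | 7.9 vs 12.5 | 29% |
| 2% vs 8% | 7.4% vs 13.1% | 5.7 points | 9.1 vs 16.0 | 46% |

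At a lower assumed risk, 0.5% vs 1%, the difference is 0.005 × 0.944 = 0.5 points. If r is equal in the two arms, it is 0. The in-hospital comparison has an expected difference of 0 in every case. Power is low throughout, so counts and an interval would tell more than a p-value.

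**The case against.** The strongest reply is that safety is not neglected. All adverse events go to an independent DSMB that can recommend changing or stopping the trial, with six-monthly meetings planned (Section 9.2). Section 3.3.2 removes many unstable patients, and Sections 2.1 and 2.2 cite safe waiting lists and safe rehabilitation in elderly and heart-failure patients. This stands against any inference that pre-operative events are ignored or that Prehab is unsafe. It does not supply a planned, reported comparison by arm.

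Four stronger readings are tempting and lack support.
- *Section 4 names these events as risks of Prehab.* It lists safety data in general. Only the twice-weekly stability check is tied to the pre-habilitation period.
- *Most of the risk lies outside the window.* An 8-day frail median stay is 8/92 = 9% of the time to discharge with the 12-week Manitoba wait, 8/70 = 11% with the 62-day preliminary wait, and 8/64 to 8/36 (12.5% to 22%) with an 8- to 4-week programme. Days are not risk, because waiting and peri-operative days need not carry equal hazard.
- *A known share of events is missed.* That needs a pre-operative rate, and none is given.
- *Ending at discharge favours the arm sent home sooner.* 30-day mortality is a named in-hospital outcome, and readmissions are collected. Their analysis is unspecified, but no bias can be sized from the documents.

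Two points of reading remain. Grammatically, in-hospital might qualify stroke alone, but the heading of Section 3.4.3 and the wording of Objective 2 point to all four events. That the surgical databases hold only operated patients is an inference, and Section 3.4.9 adds hospital charts as a source. Neither point creates an analysis of the pre-operative interval.

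**Conclusion.** The concern holds in a limited form. The only between-arm comparison of major adverse events specified in Section 5.2 covers the hospital stay, and events between randomization and surgery are collected for monitoring without any planned analysis by arm. *Only* refers to comparisons written in Section 5.2, not to every outcome named in the protocol.

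The size is unknown and may be small. The Executive Summary and Section 2.1 say that very few patients die while waiting. The differences of 0.5 to 5.7 points above follow wholly from assumed pre-operative risks and from one in-hospital rate, 4/72, seen in patients frail by the modified Fried criteria; this trial enrols from a Clinical Frailty Score of 3. What does not depend on those assumptions is that an excess before surgery would not be counted in the planned comparison. The plan should be changed on this point; the primary analysis is not in question here.

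**What to change.** In Sections 3.4.3 and 5.2, add a comparison by assigned arm, in all randomized patients, of death, MI, stroke and renal failure requiring dialysis from randomization to 30 days after surgery. For patients never operated on, set a fixed cut-off after randomization in advance. Keep in-hospital MACCE as a sub-window.

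Report the randomization-to-surgery part separately, together with new hospitalization, as counts by arm and a risk difference with 95% CI. Do not rest the conclusion on a test.

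Ascertain pre-operative events the same way in both arms, from hospital charts and from the 4-week and pre-operative visits that Section 3.6 gives to all participants. A patient who has died will not attend a visit, so the chart is needed as well. Do not use the rehabilitation team's twice-weekly checks as the source: they are described only for the pre-habilitation period, and using them could raise the Prehab count merely through closer observation. Assessors should be blinded to arm, as Section 3.5.3 already provides.

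The cost is SAP wording, one derived variable and a chart check of the pre-operative period for every randomized patient, not only those never operated on. Safety capture, chart access and both visits are already planned.
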